Network-Level Mechanisms for Preclinical Alzheimer's Disease Development

Principal Investigator: [name] (Department of Biophysics)

Co-investigator: [name] (Department of Neurology)

Address

Medical College of Wisconsin
[name]
[name]

Funding Sponsor: National Institutes of Health, National Institute on Aging (R21 AG 056882)

Version: 5

Version Date: April 1, 2019

Replaces Version: 4, September 21, 2018

PROTOCOL SUMMARY

Title	Network-Level Mechanisms for Preclinical Alzheimer's Disease Development
Principal Investigator	[name]
Study Site	Medical College of Wisconsin
Clinical Trial Phase	Phase II
Study Disease	Alzheimer's disease
Main Eligibility Criteria	
 • Fluent in English • At least 8 years of education • Healthy APOE 4 carriers and noncarriers • Age 55–75 years • Normal cognitive function • Free of neurological or psychiatric comorbidities
Study Rationale	
Levetiracetam (LEV) is a generic drug used in long-term epilepsy treatment, with known pharmacokinetic and pharmacodynamic properties. It is relatively safe and has an acceptable side-effect profile. A novel extended release formulation of AGB101 (220 mg of levetiracetam) was developed to allow for once-daily dosing in amnestic mild cognitive impairment (aMCI). So far, no studies have been conducted to see if a low dose of AGB101 can effectively reduce the network dysfunction in cognitively normal subjects who are APOE 4 carriers. The pre-dementia state among APOE 4 carriers can be identified by measuring abnormal brain connectivity with functional MRI. Considering this, use of AGB101 to reduce the network dysfunction in cognitively normal subjects who are APOE 4 carriers should be explored.

Primary Objectives	To determine whether normalization of resting-state connectivity can be achieved in APOE 4 carriers with 2 weeks AGB101 (220 mg, QD) treatment compared with APOE 4 noncarriers receiving the same treatment
Secondary Objectives	To measure cognitive function in APOE 4 carriers and noncarriers at the beginning and end of treatment with placebo

Endpoints	
 Primary outcome measurements: Network changes in the bilateral sensory motor cortex regions of the hippocampal functional connectivity after AGB101 perturbation (time frame: 2 weeks) Secondary outcome measurements: Episodic memory performance and neuropsychological test battery as assessed at baseline (Visit 1) and at the post-perturbation procedures (time frame: 2 weeks)
Study Design	
This is a randomized, double-blind, placebo-controlled crossover study in which AGB101 (220 mg, QD) or placebo will be administered to 50 healthy 55–75-year-old subjects (comprising 25 APOE 4 carriers and 25 noncarriers), with the order of treatments counterbalanced in a within-subject crossover design.
 
The study consists of prescreening (Visit –1), baseline/screening (Visit 1), a 2-week treatment period (Visit 2), a 4-week washout period (Visit 3), and a 2-week treatment period (Visit 4).

Study Agent/ Intervention Description	AGB101 Levetiracetam Extended Release 220 mg and placebo will be administered orally, QD
Number of Subjects	50, of which 25 are APOE 4 carriers and 25 are noncarriers
Subject Participation Duration	8 weeks: 2 weeks of AGB101/placebo, followed by a 4-week washout, followed by 2 weeks of AGB101/placebo
Duration of Follow up	None
Estimated Time to Complete Enrollment	18 months
Statistical Methodology	We will employ the multivariate regression model to determine the correlational changes between the hippocampal functional connectivity and the episodic memory due to AGB101 perturbation; we will assume age, years of education, gender, and gray matter volume as time-invariant covariates.
Safety Assessments	Regular data safety monitoring board meetings will be scheduled to monitor progression of the study and review drug adverse events
Efficacy Assessments	Statistically significant changes between the hippocampal functional connectivity and episodic memory relationship at baseline and at the end of the trial
Unique Aspects of this Study	This is the first study to evaluate the safety and efficacy of AGB101 to regulate brain connectivity in cognitively normal subjects at risk for dementia.

Table of Contents

1. Study Objectives	6
2. Background and Significance	7
3. Rationale	9
4. Study Design	9
5. Study Visits and Procedures	11
6. Data Management	13
7. Data Safety Monitoring Plan	14
8. References	22

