- **Enriched Testing of Subjects with APOE 4 Allele.** As stated, more than 50% of AD patients are carriers of the APOE 4 allele (4-6). The APOE 4 allele is confirmed as the most important genetic risk factor for late-onset AD. The APOE polymorphism modulates the risk of late-onset AD in an isoform-dependent manner ($\epsilon 4 > \epsilon 3 > \epsilon 2$) (49, 50). The APOE 4 allele accentuates cerebral amyloid deposition, structural and functional abnormalities, and memory decline in cognitively healthy adults. By treating APOE 4 allele carriers at high risk for AD development with a daily low dose of AGB101 (220 mg, QD) at the preclinical phase, it will be possible to determine if hyper-HFC is reduced and the memory decline is improved.

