
reversed the abnormalities in synaptic activity-related proteins. This result suggests that long-term LEV perturbation is necessary to provide the time for network adaptation and normality. As such, we designed a 2-week, low-dose LEV perturbation study to address two questions: **One**, can a low dose of LEV decrease abnormal hyper-HFC? **Two**, will the decreased functional connectivity ameliorate EM decline?

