4.1. Overall Design

This study will test the hypothesis that **decreased abnormal hyperfunctional connectivity can be correlated with improved EM using a daily, low-dose LEV perturbation (AGB101 levetiracetam extended release)**. In this study, there are two study groups: APOE 4 carriers ($n=25$) and APOE4 noncarriers ($n=25$). The functional connectivity changes in HFC will be determined in a randomized, double-blind, placebo-controlled crossover manner, in which a low dose of AGB101 levetiracetam extended release (220 mg, QD) or placebo is administered to 50 healthy 55-75-year-old subjects (comprising 25 APOE 4 carriers and 25 noncarriers), with the order of treatments counterbalanced in a within-subject crossover design, as illustrated in

Fig. 2 below. The study procedures are almost identical to those described in Refs (77, 78). In brief, study participants will receive placebo during one treatment period and AGB101 levetiracetam extended release during the other treatment period, with the order of treatments counterbalanced (randomized, double-blind).

Figure 2. Study design and AGB101 treatment protocol

Notes: Of the 50 subjects, 25 are APOE 4 carriers and 25 are noncarriers.

See Table 1 for timing and schedule of procedures.

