5.4.7. Randomization, Study Drug Dispensation, Administration, and Compliance

The Investigational Drug Service at Froedtert Hospital will randomize participants to the treatment conditions.

In Period 1, all study participants will receive treatment with either AGB101 (220 mg, orally, QD) or placebo; in Period 2, all subjects will crossover and receive the other treatment. This is a double-blind study, so both the participants and study team will be blind to the treatment received.

All study treatments (drug and placebo) are dispensed in identical nondescript tablets by the Investigational Drug Service at Froedtert Hospital. Tablets are provided for daily morning doses. Study drugs will be dispensed at baseline and on the last day of the 4-week (-/+ 1 week) washout period. Subjects will be asked to self-administer treatment QD, once in the morning.

Treatment compliance will be monitored by participant self-report at the end of each treatment phase, bottle return and pill count, and analysis of AGB101 blood values at each visit during the study protocol.

Data Management

6.1. The Froedtert Hospital Investigational Pharmacy system will be used to enroll patients and obtain the randomly assigned treatment group. Data forms will be printed, completed, and entered into a database. The database will be monitored for completeness, consistency, accuracy, and timeliness. No patient-identifying information will be stored in the database. To ensure that data are secure from external violation, computer systems containing study data will be password protected, and physical access to the computer systems will be limited.

6.2. Determination of Changes in Network Activity and Concurrent Improvement in EM. The cognitive and MRI/rfMRI datasets will be obtained at baseline (before placebo/AGB101 administration) and on the last day of each 2-week treatment period. These two time points will be denoted $t = 1, 2$. The two 25-subject groups, both of which will receive both placebo and AGB101 at different treatment phase, will be denoted $g = 1, 2$. The set of EM scores for subject s , from group g , at time t will be denoted $Cog(s,g,t)$, where $s = 1, \dots, 25$; $g = 1, 2$; and $t = 1, 2$. The HFC calculated between the hippocampus and the bilateral sensorimotor cortex for subject s , from group g , at time t will be denoted $HFC(s,g,t)$.

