6.3. Functional-Connectivity Changes Due to Perturbation. We employed age, years of education, gender, and gray matter (GM) volume as time-invariant covariates to obtain residual variables to determine the HFC changes due to perturbation. We will model the HFC as a function of these nuisance regressors, using the following multiple linear regression equation, and retain the residuals as $HFC_{Res}^+(s, g, t)$ for further analysis:

$$HFC(s, g, t) = \beta_0 + \beta_1 Age(s) + \beta_2 Edu(s) + \beta_3 GM(s) + \beta_4 CSF(s) + \beta_5 Gender(s) + Res(s, g, t),$$

where $\widetilde{HFC}^+(s, g, t) \equiv Res(s, g, t)$. This regression will be performed using all of the data (i.e., all subjects, all groups, and all times). The GM measurement will be conducted with GM concentration and hippocampal volume measurement, as described in our publication and others (71-74). We will test the residuals $\widetilde{HFC}^+(s, g, t)$ using three-factor crossed-nested analysis of variance (ANOVA), with fixed factors of group and

time and a random factor of *subject* nested within *group* (i.e., all subjects will be tested at all times, but the placebo and AGB101groups will contain different treatment phases). We will test for both group and time main effects, as well as for the group \times time interaction. If we find significant main effects or interactions, we will perform post hoc procedures to determine which time and group (i.e., placebo vs. AGB101) combinations are significantly different. In addition to the HFC analysis, we will conduct a DMN analysis 75).

6.4. EM Changes Due to AGB101Perturbation. The two EM scores (AVLT and LMT) will be normalized to Z-score by transforming individual raw test scores according to the mean and standard deviation of the scores for all subjects. Then, Z-scores of each test will be averaged to obtain individual composite memory Z-score, as we have previously published (76). Similar to the above model for HFC changes due to AGB101perturbation, we will model the Cog score, using the time-invariant covariates as nuisance regressors:

$$\Delta EM(s, g, t) = \beta_0 + \beta_1 Age(s) + \beta_2 Edu(s) + \beta_3 GM(s) + \beta_4 CSF(s) + \beta_5 Gender(s) + Res(s, g, t)$$

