5.4.7. Randomization, Study Drug Dispensation, Administration, and Compliance

The Investigational Drug Service at Froedtert Hospital will randomize participants to the treatment conditions.

In Period 1, all study participants will receive treatment with either AGB101 (220 mg, orally, QD) or placebo; in Period 2, all subjects will crossover and receive the other treatment. This is a double-blind study, so both the participants and study team will be blind to the treatment received.

All study treatments (drug and placebo) are dispensed in identical nondescript tablets by the Investigational Drug Service at Froedtert Hospital. Tablets are provided for daily morning doses. Study drugs will be dispensed at baseline and on the last day of the 4-week (-+ 1 week) washout period. Subjects will be asked to self-administer treatment QD, once in the morning.

Treatment compliance will be monitored by participant self-report at the end of each treatment phase, bottle return and pill count, and analysis of AGB101 blood values at each visit during the study protocol.

Data Management

6.1. The Froedtert Hospital Investigational Pharmacy system will be used to enroll patients and obtain the randomly assigned treatment group. Data forms will be printed, completed, and entered into a database. The database will be monitored for completeness, consistency, accuracy, and timeliness. No patient-identifying information will be stored in the database. To ensure that data are secure from external violation, computer systems containing study data will be password protected, and physical access to the computer systems will be limited.

6.2. Determination of Changes in Network Activity and Concurrent Improvement in EM. The cognitive and MRI/rfMRI datasets will be obtained at baseline (before placebo/AGB101 administration) and on the last day of each 2-week treatment period. These two time points will be denoted $t = 1, 2$. The two 25-subject groups, both of which will receive both placebo and AGB101 at different treatment phase, will be denoted $g = 1, 2$. The set of EM scores for subject s , from group g , at time t will be denoted $Cog(s,g,t)$, where $s = 1, \dots, 25$; $g = 1, 2$; and $t = 1, 2$. The HFC calculated between the hippocampus and the bilateral sensorimotor cortex for subject s , from group g , at time t will be denoted $HFC(s,g,t)$.

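### No HFC model in sections 6.2–6.3 contains both treatment and APOE genotype, so the drug effect by genotype behind the primary objective is not estimated

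*Protocol*

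**What the plan says.** The Primary Objectives row of the Protocol Summary sets carriers on AGB101 against noncarriers: "treatment compared with APOE 4 noncarriers receiving the same treatment". It does not mention placebo, and neither document gives a criterion for normalization. Elsewhere the question is the drug effect itself: section 3.2 asks "can a low dose of LEV decrease abnormal hyper-HFC", and section 2.2 says of treating carriers that "it will be possible to determine if hyper-HFC is reduced and the memory decline is improved".

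The design is a randomized placebo-controlled crossover. Under section 4.1, "study participants will receive placebo during one treatment period and AGB101 levetiracetam extended release during the other treatment period".

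The analysis is in sections 6.2 and 6.3, which the SAP repeats:

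- **Scans (6.2).** "The cognitive and MRI/rfMRI datasets will be obtained at baseline (before placebo/AGB101 administration) and on the last day of each 2-week treatment period". That is three occasions, yet they are indexed by two values of t: "and on the last day of each 2-week treatment period. These two time points will be denoted" t = 1, 2.
- **Group (6.2).** "The two 25-subject groups, both of which will receive both placebo and AGB101 at different treatment phase, will be denoted" g = 1, 2.
- **Model (6.3).** HFC is first adjusted for age, education, GM, CSF and gender. The residuals go into an ANOVA with fixed group and time, their interaction, and subject as a random factor nested in group.
- **Group again (6.3).** A significant result leads to "post hoc procedures to determine which time and group (i.e., placebo vs. AGB101) combinations are significantly different".

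**The concern.** A crossover in two genotype groups can measure three things directly: the AGB101-minus-placebo effect in carriers (dC), the same effect in noncarriers (dN), and their difference. Estimating them by genotype requires a model that knows which treatment each scan followed and which genotype each subject has. As written, the HFC model has one factor called group, and it cannot be both.

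The two definitions of group also conflict. If each group receives both treatments, group is not treatment. If group is treatment, subject cannot be nested in it, because every subject appears under both levels.

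The objective adds a second ambiguity. The drug effect in carriers, the genotype difference in drug effect, and the gap remaining between treated carriers and untreated noncarriers are different answers, and the plan does not say which decides. If this is settled only when the data are analysed, the deciding contrast could be chosen after the results are seen.

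**Working it through.** The plan states no power, alpha or effect size for the 50 subjects, so there is no figure to reproduce. The check is what each reading of group and time estimates.

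**Notation.** dC and dN are as above. pC and pN are the changes from baseline to the placebo scan in carriers and noncarriers (placebo response plus any rescan effect). Treatment order is taken as balanced within genotype, and there is no carryover.

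**Group × time under each reading**

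1. *Group = genotype; t = baseline versus both period scans, pooled equally.* The mean change in carriers is pC + dC/2, because one of the two period scans is on drug. In noncarriers it is pN + dN/2. The interaction is (dC − dN)/2 + (pC − pN), and the time effect within carriers is dC/2 + pC. Example with assumed values dC = −0.8 and dN = 0: if pC = pN, the result is −0.40; if carriers alone change by −0.3 on placebo, it is −0.40 − 0.30 = −0.70, with the same drug effect.
2. *Group = genotype; t = Period 1 versus Period 2.* Half of each genotype moves from drug to placebo and half from placebo to drug, so the drug effect cancels and the interaction is 0. Twenty-five cannot be halved; a 13/12 split leaves 1/25 = 0.04 of each genotype's drug effect.
3. *Group = sequence; t = period.* Half the interaction contrast is (dC + dN)/2. Genotype is absent.
4. *Group = treatment; t = baseline versus post.* The interaction is (dC + dN)/2. Genotype is absent and the nesting is impossible.

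None gives dC, dN or dC − dN. Post hoc comparisons do not help, because they compare cells of the same group and time factors.

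**The objective's comparison.** Let G be the off-drug carrier-minus-noncarrier gap.

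- Carriers on drug minus noncarriers on drug: G + dC − dN.
- Carriers on drug minus noncarriers off drug: G + dC.
- The two differ by exactly dN. With G = 1 (assumed), no drug effect gives an on-drug gap of 1, and a fall of 1 in both genotypes also gives 1.

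**Illustrative precision.** Every input except n = 25 per genotype is assumed: two-sided alpha 0.05, single-scan SD 1, correlation 0.5 among the three scans, dC = −0.8, dN = 0, pC = pN. Power is from the noncentral t.

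- Treatment × genotype: SD of AGB101 − placebo = √(2 × 0.5) = 1.000; noncentrality 0.8/(1.000 × √(2/25)) = 2.83, 48 df; power 0.79.
- Reading 1, as a two-sample test on change scores: SD = √(1.5/2 + 1 − 1) = 0.866; noncentrality 0.4/(0.866 × √(2/25)) = 1.63, 48 df; power 0.36. Simulating the nested ANOVA on all three scans (98 residual df) gives slightly less, about 0.3.
- With noncarriers responding half as much: 0.28 and 0.13.
- For dC from −0.5 to −1.0, correlations 0.3 to 0.7 and dN = 0: 0.31–0.99 and 0.135–0.733.
- AGB101 minus placebo within 25 carriers: noncentrality 0.8 × √25/1.000 = 4.0, 24 df; power 0.97. This answers a different question, so its excess over 0.79 is not a loss caused by the objective.
- 95% CI half-width for a 25 versus 25 gap: t(0.975, 48) × √(2/25) = 2.011 × 0.283 = 0.57 SD.

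**The case against.** **Treatment is in the model, because 6.3 says group is placebo versus AGB101.** This stands in part. A reader might infer that the plan has no treatment factor at all, and the documents do not support that: on the 6.3 wording an all-subject drug effect is available. But that wording contradicts 6.2 and the nesting, and accepting it removes genotype.

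**The ANOVA could be run on baseline and the AGB101 scan only.** Group × time would then be (dC − dN) + (pC − pN), which is the wanted difference only if placebo and rescan changes are equal across genotypes. It would also ignore the placebo data. The text does not describe this analysis.

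**Section 6.5 has a treatment indicator.** It does, but the outcome there is episodic memory, the HFC term is baseline HFC, and there is no genotype term.

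**The objective's comparison is legitimate.** Comparing the two drug responses is a valid test of genotype specificity, and placebo control is stated in the Study Design row, Specific Aim 1 and section 4.1. A reader might infer that the trial lacks a placebo comparison; it does not. The omission is confined to the objective's wording, and the dN shift vanishes if noncarriers do not respond. The documents give no data either way.

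**The planned interaction recovers half the genotype difference.** That is tempting as a flat statement, but it holds only under reading 1 with equal placebo and rescan change. Section 6.2 never says that g is genotype, and its wording also fits sequence groups.

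**Conclusion.** The concern holds as an internal inconsistency in the analysis text. Group has two incompatible definitions, three scans are coded as two time points, and no HFC model in 6.2–6.3 contains both treatment and genotype. On none of the readings the text supports does the planned ANOVA estimate the AGB101-minus-placebo effect in carriers, in noncarriers, or their difference. This follows from the model terms and needs no numerical assumption. The expressions for individual readings rest on treatment order balanced within genotype and no carryover.

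The mismatch in the objective is a separate, smaller point, with size exactly dN.

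The power figures show only that the choice of coding can matter. The documents report neither an HFC gap between genotypes nor its SD or correlation, so the figures do not measure a loss in this trial. The planned data are sound for the purpose: scans at Visits 1, 2 and 4 with counterbalanced order can support the right analysis. It should be settled before unblinding.

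**What to change.** In 6.2–6.3 of both documents, replace the group and time coding with one mixed model for HFC. Give treatment, period, sequence, APOE group and treatment × APOE group separate terms, make subject random within sequence and APOE group, and keep baseline distinct from the two period scans.

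Reword the primary objective to match. Name the AGB101-minus-placebo difference within carriers as the deciding contrast, and report treatment × APOE group beside it as the test of genotype specificity. Say in advance how the two are read together.

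If normalization is kept, describe it by the gap between carriers on AGB101 and noncarriers on placebo, with a 95% CI. Do not infer normalization from a non-significant gap.

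The cost is wording and model specification, with no added scans or visits. There are two downsides. The carrier contrast alone does not show genotype specificity. The gap is imprecise (half-width about 0.57 SD at 25 versus 25), mixes genotype with drug, and needs treatment order near-balanced within genotype, which the documents do not state.

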1. STUDY OBJECTIVES

Neuropathological, structural, and functional changes related to Alzheimer's disease (AD) may begin insidiously, 20 to 30 years before the manifestation of clinical symptoms. This long, preclinical phase of AD provides a critical window of opportunity to conduct early disease intervention. In this study, we will **test our hypothesis that, during the preclinical AD developmental phase in cognitively normal (CN) older subjects with the apolipoprotein E ε4 (APOE 4) allele, decreased abnormal hyperfunctional connectivity can be correlated with improved episodic memory (EM) using a perturbation, such as AGB101 low dose levetiracetam extended release formulation**. The major pieces of foundational evidence that support our hypothesis are described below.

